### **Adverse Reaction (AR)**

An AR is a response to a medicinal product which is noxious and unintended.

Response in this context means that a causal relationship between a medicinal product and an AE is at least a reasonable possibility.

ARs may arise from use of the product within or outside the terms of the marketing authorization or from occupational exposure. Conditions of use outside the marketing authorization include off-label use, overdose, misuse, abuse, and medication errors.

### **Reports of Special Situations: Pregnancy, Overdose, Off-label use, Misuse, Medication Error or Occupational Exposure, Lack of Therapeutic Efficacy, and Others**

- Use of a medicinal product during pregnancy or breastfeeding: reports where embryo, fetus, or child may have been exposed to medicinal products (either through maternal exposure or transmission of a medicinal product via semen following paternal exposure)
- Reports of overdose, abuse, off-label use, misuse, medication error, or occupational exposure
- Lack of therapeutic efficacy
- Prescription error/dispensing error, (e.g., due to confusion of invented names of the medicinal products)
- Drug interaction
- Suspected transmission of an infectious agent via a medicinal product
- Product complaints, including falsified product or counterfeit

Reports of special situation with no associated AR will not be submitted to the authorities as individual case safety reports. They will be collected and considered in the study report or any interim reports, as applicable.

### **Serious Adverse Event (SAE)/Serious Adverse Reaction (SAR)**

An SAE/SAR is any AE/AR as defined above, which also fulfills at least one of the seriousness criteria below:

- Results in death
- Is life-threatening
- Requires in-patient hospitalization or prolongation of existing hospitalization
- Results in persistent or significant disability/incapacity
- Is a congenital anomaly/birth defect
- Is otherwise considered as medically important

 Life-threatening in this context refers to a reaction in which the patient was at risk of death at the time of the reaction; it does not refer to a reaction that hypothetically might have caused death if more severe.

 Medical and scientific judgment should be exercised in deciding whether other situations should be considered as serious reactions, such as important medical events (IMEs) that might not be immediately life-threatening or result in death or hospitalization but might jeopardize the patient or might require an intervention to prevent one of the other outcomes listed above. Such IMEs should be considered as serious.

Examples of such events are intensive treatment in an emergency room or at home for allergic bronchospasm, blood dyscrasias, or convulsions that do not result in hospitalization or development of dependency or abuse. As a guidance, the IME terms list is intended to be used for assessment of suspected ARs (see EMA/207865/2017).

Any suspected transmission via a medicinal product of an infectious agent is also considered a SAR.

### Events Not to be Considered as AEs

Medical conditions present and documented at study start, which do not worsen in severity or frequency during the study are defined as Baseline Medical Conditions and elective procedures and are NOT to be considered AEs.

## 11.2 Severity of Adverse Events

Investigators should assess the severity/intensity of any AE as follows:

**Mild:** The subject is aware of the event or symptom, but the event or symptom is easily tolerated.

**Moderate:** The subject experiences sufficient discomfort to interfere with or reduce his or her usual level of activity.

**Severe:** Significant impairment of functioning: the subject is unable to carry out usual activities.

Investigators are required to grade the severity/intensity of each AE (including serious) recorded. In oncology indications, investigators will reference the NCI-CTCAE, current version 5.0 (publication date: 27 November 2017). This is a descriptive terminology with 5 Grades: Grade 1 (Mild), Grade 2 (Moderate), Grade 3 (Severe), Grade 4 (Life-threatening) and Grade 5 (Death due to AE).

Note: *NCI-CTCAE Grade 4 or 5*

If events are graded in accordance to the NCI-CTCAE criteria, then all AEs with severity Grade 4 or 5 should be classified as serious. Exception: Asymptomatic Grade 4 laboratory abnormalities (e.g., Grade 4 anemia, Grade 4 neutropenia) may be considered non-serious, if not meeting any of the above seriousness criteria.

If the severity/intensity of a particular AE cannot be specifically graded by NCI-CTCAE, the investigator is to revert to the general definitions of Grade 1 through Grade 5 and use his or her best medical judgment grading the AE according to the Qualitative Toxicity Scale below:

**Grade 1** (mild): asymptomatic or mild symptoms; clinical or diagnostic observations only; intervention not indicated.

**Grade 2** (moderate): Moderate; minimal, local or noninvasive intervention indicated; limiting age-appropriate instrumental activities of daily living (ADL).

**Grade 3** (severe): Severe or medically significant but not immediately life-threatening; hospitalization or prolongation of hospitalization indicated; disabling; limiting selfcare ADL. Significant impairment of functioning: the subject is unable to carry out usual activities.

**Grade 4** (life-threatening): Life-threatening consequences; urgent intervention indicated.

**Grade 5** (fatal): AE with fatal outcome

### 11.3 Causality Assessment

Investigators must assess the causal relationship between AEs and study drug (including any other non-medicinal product, radiation therapy, etc.) considering temporal relationship between the AE onset and study drug administration, safety profile of study drug (known ARs), the patient's condition (medical history, underlying disease), concomitant medication, and study procedures.

**Related:** Suspected to be reasonably related to any study medication.

**Not related:** Not suspected to be reasonably related to any study medication. A reasonable alternative explanation must be provided.

### 11.4 Collection and Recording of Adverse Events

The recording period for AEs begins when the subject is initially included in the study (date of signature of first informed consent) and continues to at least end of the mandatory safety-follow-up period (90 days post discontinuation of Avelumab plus Axitinib therapy or completion of the 24 months (i.e., end of the study) follow-up from the index date, whichever occurs first).

All safety data, as specified above, occurring during the study, must be documented by the investigator within 24 hours of awareness and recorded in the eCRF, including its description, seriousness, severity (grading), duration (onset and resolution dates), causal relationship, any other potential causal factors, actions taken with the study drug (e.g., dose reduction, withdrawal), required treatment, and outcome of the AE.

Note: *Event term 'Death', 'Disability' and 'Hospitalization'*

Death, disability, and hospitalization are considered outcomes in the context of safety reporting and not usually considered ARs/AEs. Therefore, the primary cause of death, disability, or hospitalization should be recorded and reported as an SAE/AR, and the outcome should be recorded in a separate data field. However, a term for the outcome will be selected if it is the only information reported or provides significant clinical information.

If death occurs, the primary cause of death or event leading to death should be recorded and reported as an SAE. “Fatal” will be recorded as the outcome of this respective event and not as a separate event. Only if no cause of death can be reported (for example, sudden death, unexplained death), the death per se might then be reported as an SAE.

All SAEs/AEs due to Avelumab as well as Axitinib will be collected in the study database.

**Reports of Special Situations (see definition)** are also to be recorded in the eCRF following the AE procedure, even if occurring without AE.

**Pregnancy and Breastfeeding.** Pregnancy or breastfeeding must be recorded in the eCRF and additionally be reported to the Sponsor immediately (within 24 hours of awareness) by using separate paper data collection forms for pregnancy, independent if an AE was reported or not. The outcome of the pregnancy should be followed up and reported to the Sponsor until delivery.

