**Table 1. Schedule of Assessments**

Assessment	Screening visit	W0 (Index date/ Baseline visit)	Follow-up visits (between W0 to W104) as per routine clinical practice	W104 (end of study)
Informed consent	X			
Inclusion/exclusion criteria	X	X		
Demographics (year of birth, gender)		X		
Physical examination/ vital signs a		X		
Body weight a		X	X	X
Concomitant diseases b		X		
Concomitant medications c		X	X	X
Cancer history d		X		
ECOG performance status		X		
MSKCC risk group e		X		
IMDC risk group f		X		
HRQoL using the NCCN-FACT Fksi-19 questionnaire g		X	X	X
Safety assessment	X	X	X	X
Avelumab plus Axitinib therapy h		X	X	X
Second-line treatment (if Avelumab plus Axitinib discontinued)			X	X
Third-line treatment (if second-line treatment discontinued)			X	X
Treatment response i			X	X
Treatment for AE related to Avelumab plus Axitinib therapy j		X	X	X

AE=Adverse event, ECOG=Eastern Cooperative Oncology Group, HRQoL=health-related quality of life, IMDC=International Metastatic RCC Database Consortium, MSKCC=Memorial Sloan-Kettering Cancer Center, NCCN-FACT Fksi-19=National Comprehensive Cancer Network/Functional Assessment of Cancer Therapy-Kidney Symptom Index 19, W=Week

a Results from physical examinations, vital signs, and body weight will be collected upon availability. Physical examination includes an examination of major body systems. Vital signs include blood pressure (systolic and diastolic) and pulse rate.

b Information on concomitant diseases such as autoimmune disease, cardiovascular disease, hypertension, renal failure, and liver disease.

c Information on concomitant medications such as the use of corticosteroids, anticoagulants, and antibiotics.

d Information on cancer history: age at diagnosis, tumor, node, metastasis (TNM) stage, location of metastases, received nephrectomy, other prior cancer therapies and procedures, expression of the programmed death ligand 1 (PD-L1).

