## 9.2.5 Withdrawal from the Study

Patients are free to withdraw from the study at any time without giving their reasons. Patients who discontinue treatment will continue to be followed up until end of the study, as per Schedule of Assessments ([Table 1](#)), regardless of treatment status.

A patient is considered lost to follow-up after 2 documented failed attempts to reach out to the patient. If a patient is lost to follow-up, adequate effort must be made by study center personnel to contact the patient and determine the reason for discontinuation. The measures taken to follow-up on the patient must be documented. If a patient withdraws before completion of study procedures (as described in the Schedule of Assessments in [Table 1](#)), the reason for withdrawal shall be documented in source documents and in the eCRF.

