To analyze the nature, severity, duration, frequency, and timing of Adverse Events (AEs) that occurred from the index date up to 90 days post discontinuation of Avelumab plus Axitinib or completion of the 24 months (ie, end of the study) follow-up from the index date, whichever occurs first	Endpoint: Frequency and nature of all-cause AEs according to Medical Dictionary for Regulatory Activities (MedDRA) system organ class (SOC) and preferred term (PT) that occurred from the index date up to 90 days post discontinuation of Avelumab plus Axitinib or completion of the 24 months (ie, end of the study) follow-up from the index date, whichever occurs first.	15.1.1
To assess time to therapy discontinuation due to AE \geq Grade 3	Endpoint: Duration of Avelumab plus Axitinib therapy among patients who discontinued the study drugs due to all-cause AEs \geq Grade 3.	15.1.2
To assess therapy modifications due to AE related to Avelumab plus Axitinib therapy and management of AE related to Avelumab plus Axitinib therapy	Endpoint: Percentage of patients with therapy modifications due to AE related to Avelumab plus Axitinib therapy (eg, therapy interruptions and reductions of infusion rate for Avelumab, therapy interruptions, and dose reductions for Axitinib).	15.1
To determine percentage of patients receiving later-line therapy and frequency distribution of later-line therapy regimes among patients progressing on Avelumab plus Axitinib	Endpoint: Percentage of patients receiving later-line therapy and frequency distribution of later-line therapy regimes among patients progressing on Avelumab plus Axitinib including the names of medications of monotherapy/combination treatment used in second-line and third-line therapy.	15.1
To assess time to second-line therapy initiation (T2LT)	Endpoint: Time interval from Avelumab plus Axitinib therapy discontinuation to the initiation of second-line therapy.	14.2
To assess patient-reported potential signs and symptoms of immune-related AEs	Endpoint: Frequency of patient-reported signs and symptoms of potential immune-related AEs. Immune-related AEs may include immune-mediated pneumonitis, immune-mediated colitis, immune-mediated hepatitis, immune-mediated endocrinopathies, immune-mediated nephritis with renal dysfunction.	15.2.3

6 Overview of Planned Analyses

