15.2.2 Serious Adverse Events

The following overall frequency tables will be prepared for serious AEs:

- Incidence of serious AEs by SOC and PT
- Incidence of related serious AEs by SOC and PT
- Incidence of serious NCI-CTCAE [version 5.0]) Grade ≥ 3 by SOC and PT
- Incidence of serious AEs leading to death by SOC and PT

The listings of serious adverse events (SAEs) will also be provided with the relevant information:

- Patient number
- Age (yrs.)/ Sex/ Weight (kilograms)
- Start date/ End date
- Seriousness criteria
- Is a TEAE? (Yes/No)
- Relationship with Avelumab (Not Related/ Related)
- Relationship with Axitinib (Not Related/ Related)

For the seriousness criteria report all that apply: Results in death, Is life-threatening, Requires/prolongs hospitalization, Persistent/significant disability/incapacity, Is a congenital anomaly/birth defect, Other medically important condition.

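### The four serious-AE frequency tables in SAP 15.2.2 have no onset window, so they can count events outside the stated AE endpoint, and no SAE table matches that endpoint

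*Protocol*

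**What the plan says.** **Endpoint window.** Protocol 9.1.2.2 and SAP section 5 count AEs "that occurred from the index date up to 90 days post discontinuation of Avelumab plus Axitinib or completion of the 24 months", whichever comes first.

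**Recording period.** Protocol 11.4 begins at signature of the first informed consent. It then "continues to at least end of the mandatory safety-follow-up period", and defines that mandatory period as ending 90 days after discontinuation or at 24 months, whichever is first. No maximum is given.

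**Schedule.** In Protocol Table 1 the row "Safety assessment" is marked at screening, Week 0, the follow-up visits and Week 104. It has no footnote tying it to the 90-day point. Protocol 9.2.5 adds: "Patients who discontinue treatment will continue to be followed up until end of the study, as per Schedule of Assessments", whatever the treatment status.

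**Analysis.** SAP 15.1 bases the analyses of that section on TEAEs unless otherwise stated. SAP 9.8 closes the on-treatment period at the earliest of last dose plus 30 days, cut-off, death and the day before subsequent anti-cancer drug therapy. SAP 15.2.2 is outside section 15.1 and reads: "The following overall frequency tables will be prepared for serious AEs". The first table is "Incidence of serious AEs by SOC and PT". The others cover related, Grade 3 or higher, and fatal serious AEs. None has a start or end date.

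**The concern.** The stated endpoint is closed at both ends, but the four tables in SAP 15.2.2 take whatever was recorded up to the data cut-off (SAP 9.1). Recording may start before the index date and has only a minimum end. A site that stops at 90 days and a site that continues to Week 104 could both claim to follow the protocol. The SAE percentages would then rest partly on how long each site recorded, and could include events during second- or third-line therapy.

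Protocol 11.5 adds a related difficulty. Fatal disease progression becomes reportable as an (S)AE when it falls within the reporting period of 11.4. If sites read the end of that period differently, the same late progression death could be an SAE at one site and not at another. That bears directly on the 15.2.2 table of serious AEs leading to death.

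At stake is the interpretation of a secondary safety output in a descriptive study of about 100 patients at about 30 sites. The primary endpoint, 12-month OS, is not affected.

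**Working it through.** The documents state no SAE rate on this point, so there is no figure to reproduce. The check sets the windows side by side and then illustrates the gap.

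**1. Windows compared**

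| Item | Opens | Closes |
|---|---|---|
| AE endpoint (Protocol 9.1.2.2, SAP 5) | Index date | Earlier of 90 days after discontinuation and 24 months |
| AE recording (Protocol 11.4) | Consent | At least the same point; no maximum |
| Safety row of Table 1, with 9.2.5 | Screening | Week 104 |
| Serious TEAEs (SAP 15.1.1, 9.8) | Index date | Last dose + 30 days, or earlier cut-off, death or day before new anti-cancer drug |
| Serious AEs (SAP 15.2.2) | Not stated | Not stated |

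The TEAE tables are narrower than the endpoint and the 15.2.2 tables are unbounded. No SAE table uses the endpoint window.

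**2. Does 15.2.2 mean TEAEs?** SAP 15.1.1 already orders serious, serious related, serious Grade 3 or higher, and serious fatal TEAEs by SOC and PT. Read as TEAEs, the four 15.2.2 tables would duplicate those. The natural reading is all recorded SAEs.

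**3. Who is affected.** With 30.4375 days per month (SAP 9.5), Week 104 is 728 / 30.4375 = 23.9 months and 90 days is 90 / 30.4375 = 2.96 months. Extra time open to recording = 23.92 - (month of stopping + 2.96), if positive.

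- Stop at month 6: 23.92 - 8.96 = 15.0 months
- Stop at month 12: 23.92 - 14.96 = 9.0 months
- Stop at month 18: 23.92 - 20.96 = 3.0 months
- The excess reaches zero at 23.92 - 2.96 = 20.96, about month 21

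**4. Illustrative person-time.** Assumptions, none given in the documents: exponential time on treatment with median 8 or 14 months; exponential death with 12-month OS of 80% or 90%; 24-month follow-up; 90 days taken as 3 months; no withdrawal or loss to follow-up. With T the time to stopping and D the time to death: end = min(D, 24); in-window time = min(T + 3, end); post-window time = end minus in-window time.

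| Median on treatment | 12-month OS | In-window (months) | Post-window (months) | Ratio | Patients with post-window time |
|---|---|---|---|---|---|
| 8 | 80% | 10.9 | 8.4 | 0.77 | 69% |
| 8 | 90% | 11.8 | 9.9 | 0.84 | 77% |
| 14 | 80% | 13.5 | 5.9 | 0.44 | 52% |
| 14 | 90% | 14.8 | 6.9 | 0.47 | 58% |

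The ratio compares a site recording fully to month 24 with one stopping exactly at 90 days. It measures observation time. It does not measure bias in an SAE percentage.

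**5. Illustrative SAE proportions.** Turning time into proportions needs an SAE hazard r, assumed constant after treatment stops. Ignoring deaths, the proportion is the mean of 1 - exp(-r × time observed). With median time to discontinuation set at 13.8 months (the median PFS that Protocol section 7 quotes for the combination, used as a stand-in), r = 0.01, 0.02 and 0.04 per month give 14.5%, 26.4% and 44.6% within the endpoint window, against 21.3%, 38.0% and 61.6% to Week 104. Ignoring deaths and holding the hazard constant makes these gaps upper-end figures.

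**The case against.** The strongest reply is that the recording period is defined. Protocol 11.4 states the mandatory period, Protocol 9.1.1 plans a safety follow-up at 90 days after discontinuation, and 11.5 refers back to 11.4 as setting the period. Other rows of Table 1, such as study therapy and HRQoL, are also marked to Week 104 although they depend on treatment status, and patients still on treatment at Week 104 need a mark there. This stands as far as it goes. A reader might infer that Table 1 requires recording to Week 104, or that sites will in fact record different periods; the documents show neither. They permit recording beyond 90 days and can be read as scheduling it.

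Second, a treatment-focused SAE analysis exists. The serious-TEAE tables exclude events after a new anti-cancer drug starts, and the SAE table in the SAP's primary-analysis output list is TEAE-based. All-SAE tables beside them could be a deliberate complement. This limits the harm, and it rules out the inference that every SAE output is unbounded. It does not supply a table on the 90-day window.

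Third, a reader might take SAEs between consent and the index date for pre-treatment events that contaminate a toxicity rate. They are not. Inclusion criterion 5 requires 1 or 2 cycles already received, and the index date is the first administration after consent, so these patients are already on the combination. The events are outside the endpoint window but may well be treatment toxicity.

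Fourth, the treatment-emergent flag in the 15.2.2 listing proves little about the frequency tables, because SAP 15.1 already puts all AEs in the listings. Protocol 11.5 also exempts most progression from SAE reporting, and the related-SAE table is filtered by causality. These points reduce the likely number of late events without giving the tables a window.

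**Conclusion.** The point holds as a mismatch between definitions. Followed as written, the four SAP 15.2.2 tables can count SAEs outside the stated endpoint window, including SAEs during later-line therapy. At the late end this needs two conditions: the patient stops before about month 21, and the site records beyond 90 days. The serious-TEAE tables reduce the consequence, but no SAE table is defined on the stated endpoint.

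The size is unknown. The 44-84% range of extra observation time rests on assumed treatment duration and survival and contrasts two extremes of site practice, so it is an upper-end illustration. It should not be read as an expected inflation of the SAE rate, nor do the documents show that the percentages will be misread as toxicity of the combination. This is a worthwhile low-cost correction to a secondary safety output.

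**What to change.** - In SAP 15.2.2, limit the four frequency tables to SAEs with onset from the index date to the earlier of 90 days after discontinuation and 24 months, as in Protocol 9.1.2.2 and SAP section 5.
- Show SAEs with onset after that window in a separate table or listing.
- Show SAEs between consent and the index date separately as well, labelled as occurring in patients already receiving avelumab plus axitinib and not as pre-treatment events.
- Reconcile the open-ended wording of Protocol 11.4 with Table 1 and 9.2.5 so that all sites record the same period. The reporting period that 11.5 relies on for fatal progression is then also unambiguous.

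A second-line therapy started within 90 days of stopping still falls inside the endpoint window; the serious-TEAE tables remain the ones that exclude it.

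The cost is a short addition to SAP 15.2.2, one date filter and one protocol clarification. No recorded data are discarded. The downside is a smaller headline SAE count and one extra listing.

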## 11.5 Safety Data Reporting

### Safety Data Collection Forms:

The following safety data collection forms are used in this study:

- (Serious) Adverse Event Report Form
- Pregnancy Report Form
- Parent-Child/Fetus AE Report Form

